9.4.6. Hepatitis B Virus (HBV) DNA Monitoring

Patients who were hepatitis B core antibody positive at screening for the originating study will continue to require Hepatitis B virus (HBV) DNA monitoring approximately every 3 months up to Week 60, thereafter reducing to every 6 months, regardless of their hepatitis B surface antibody status.

The following actions should be taken in response to HBV DNA test results:

- If a single result is obtained with a value “below limit of quantitation,” the test should be repeated within approximately 2 weeks.
- If the repeat test result is “target not detected,” monitoring may resume according to the study schedule.
- If the patient has 2 or more test results with a value “below limit of quantitation” during the study, HBV DNA testing should be performed approximately once per month for the remainder of the study and referral to a hepatologist is recommended.
- If a result is obtained with a value above limit of quantitation at any time during the study, the patient will be permanently discontinued from investigational product (see Section 8.1.1) and should be referred to a hepatology specialist immediately.
 - In selected cases, investigators may temporarily continue investigational product in accordance with current immunomodulator management in the setting of HBV DNA positivity. This option may be considered in consultation with Lilly (or its designee) and after evaluation of individual patient risks and benefits.

9.4.7. Hepatic Safety Monitoring

If a study patient experiences elevated ALT ≥ 3 x ULN, ALP ≥ 2 x ULN, or elevated TBL ≥ 2 x ULN, liver testing ([Appendix 4](#)) should be repeated within 3 to 5 days, including ALT, AST, ALP, TBL, direct bilirubin, gamma-glutamyl transferase, and creatine kinase to confirm the abnormality and to determine if it is increasing or decreasing. If the abnormality persists or worsens, clinical and laboratory monitoring should be initiated by the investigator and in consultation with the study medical monitor. Monitoring of ALT, AST, TBL, and ALP should continue until levels normalize or return to approximate baseline levels.

Discontinuation criteria of investigational products, either temporary interruption or permanent discontinuation, due to abnormal ALT, AST, TBL, or ALP, are detailed in Section 8.1.

Hepatic Safety Data Collection

Additional safety data should be collected via the eCRF if 1 or more of the following conditions occur:

- Elevation of serum ALT to ≥ 5 x ULN on 2 or more consecutive blood tests
- Elevated serum TBL to ≥ 2 x ULN (except for cases of known Gilbert's syndrome)
- Elevation of serum ALP to ≥ 2 x ULN on 2 or more consecutive blood tests
- Patient discontinued from treatment due to a hepatic event or abnormality of liver tests
- Hepatic event considered to be a SAE

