8.1. Discontinuation from Study Treatment

8.1.1. Temporary Interruption of Investigational Product

In some circumstances, it may be necessary to temporarily interrupt treatment as a result of AEs or abnormal laboratory values that may have an unclear relationship to investigational product. It is recommended that the investigator consult with Lilly (or its designee) before temporarily interrupting therapy for reasons other than those defined in [Table JAIM.4](#). Retest timing and frequency is at the investigator's discretion.

Investigational product that was temporarily interrupted because of an AE or abnormal laboratory value, not specifically covered in [Table JAIM.4](#), may be restarted at the discretion of the investigator. Investigational product must be held in the following situations and may only be resumed as noted in the table.

Table JAIM.4. Criteria for Temporary Interruption of Investigational Product

Hold Investigational Product if the Following Abnormalities Occur:	Investigational Product May be Resumed When:
WBC count <2000 cells/ μ L ($<2.00 \times 10^3/\mu$ L or <2.00 GI/L)	WBC count ≥ 2500 cells/ μ L ($\geq 2.50 \times 10^3/\mu$ L or ≥ 2.50 GI/L)
ANC <1000 cells/ μ L ($<1.00 \times 10^3/\mu$ L or <1.00 GI/L)	ANC ≥ 1200 cells/ μ L ($\geq 1.2 \times 10^3/\mu$ L or ≥ 1.2 GI/L)
Lymphocyte count <300 cells/ μ L ($<0.30 \times 10^3/\mu$ L or <0.30 GI/L)	Lymphocyte count ≥ 500 cells/ μ L ($\geq 0.50 \times 10^3/\mu$ L or ≥ 0.50 GI/L)
Platelet count <25,000/ μ L ($<25 \times 10^3/\mu$ L or <25 GI/L)	Platelet count $\geq 50,000/\mu$ L ($\geq 50 \times 10^3/\mu$ L or ≥ 50 GI/L)
eGFR <40 mL/min/1.73 m ² for patients with eGFR ≥ 60 mL/min/1.73 m ²	eGFR ≥ 50 mL/min/1.73 m ²
ALT or AST >5 x ULN	ALT and AST return to <2 x ULN and possible DILI has been ruled out, and IP is not considered to be the cause of enzyme elevation
Hemoglobin <8 g/dL (<80.0 g/L)	Hemoglobin ≥ 9 g/dL (≥ 90.0 g/L)
Symptomatic herpes zoster	All skin lesions have crusted and are resolving
Infection that, in the opinion of the investigator, merits the IP being withheld ^a	Resolution of infection that, in the opinion of the investigator, merits the IP being restarted

Abbreviations: ALT = alanine aminotransferase; ANC = absolute neutrophil count; AST = aspartate aminotransferase; eGFR = estimated glomerular filtration rate; IP = investigational product; ULN = upper limit of normal; WBC = white blood cell.

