^a Permanent discontinuation of IP should be considered for patients who develop a serious infection that, in the opinion of the investigator, would pose an unacceptable risk if IP were resumed.

8.1.2. **Permanent Discontinuation from Study Treatment**

Possible reasons leading to permanent discontinuation of investigational product:

- **Subject Decision**
 - The patient requests to discontinue investigational product.
- **Investigator Decision**
 - The investigator decides that the patient should be discontinued from investigational product.
- **Discontinuation due to a hepatic event or liver test abnormality.** Patients who are discontinued from investigational product due to a hepatic event or liver test abnormality should have additional hepatic safety data collected via eCRF.

Discontinuation of the investigational product for abnormal liver tests **should be** considered by the investigator when a patient meets one of the following conditions after consultation with the Lilly-designated medical monitor:

- ALT or AST >8 x upper limit of normal (ULN)
- ALT or AST >5 x ULN for more than 2 weeks after temporary interruption of investigational product
- ALT or AST >3 x ULN and either total bilirubin level (TBL) >2 x ULN or international normalized ratio >1.5
- ALT or AST >3 x ULN, with the appearance of fatigue, nausea, vomiting, right upper-quadrant pain or tenderness, fever, rash, and/or eosinophilia (>5%)
- Alkaline phosphatase (ALP) >3 x ULN
- ALP >2.5 x ULN and TBL >2 x ULN
- ALP >2.5 x ULN, with the appearance of fatigue, nausea, vomiting, right quadrant pain or tenderness, fever, rash, and/or eosinophilia (>5%)
- **Discontinuation due to Other Laboratory Abnormalities:**
 - White blood cell count <1000 cells/ μ L (1.00x10³/ μ L or 1.00 GI/L)
 - Absolute neutrophil count <500 cells/ μ L (0.50x10³/ μ L or 0.50 GI/L)
 - Lymphocyte count <200 cells/ μ L (0.20x10³/ μ L or 0.20 GI/L)
 - Hemoglobin <6.5 g/dL (<65.0 g/L)

Temporary interruption rules (see Section 8.1.1) must be followed where applicable. For lab values that meet permanent discontinuation thresholds, investigational product should be discontinued. However, if in the opinion of the investigator, the lab abnormality is due to intercurrent illness or another identified factor, lab tests may be repeated. The investigator may be able to restart investigational product after consultation with the Lilly-designated medical

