Appendix 4. Hepatic Monitoring Tests for Treatment-Emergent Abnormality

Selected tests may be obtained in the event of a treatment-emergent hepatic abnormality and may be required in follow-up with patients in consultation with the Lilly, or its designee, clinical research physician.

Hepatic Monitoring Tests

Hepatic Hematology^a

Hemoglobin
Hematocrit
RBC
WBC
Neutrophils, segmented
Lymphocytes
Monocytes
Eosinophils
Basophils
Platelets

Hepatic Chemistry^a

Total bilirubin
Direct bilirubin
Alkaline phosphatase
ALT
AST
GGT
CPK

Haptoglobin^a

Hepatic Coagulation^a

Prothrombin Time
Prothrombin Time, INR

Hepatic Serologies^{a,b}

Hepatitis A antibody, total
Hepatitis A antibody, IgM
Hepatitis B surface antigen
Hepatitis B surface antibody
Hepatitis B Core antibody
Hepatitis C antibody
Hepatitis E antibody, IgG
Hepatitis E antibody, IgM

Anti-nuclear antibody^a

Alkaline Phosphatase Isoenzymes^a

Anti-smooth muscle antibody (or anti-actin antibody)^a

Abbreviations: ALT = alanine aminotransferase; AST = aspartate aminotransferase; CPK = creatinine phosphokinase; GGT = gamma-glutamyl transferase; Ig = immunoglobulin; INR = international normalized ratio; RBC = red blood cells; WBC = white blood cells.

^a Assayed by Lilly-designated or local laboratory.

^b Reflex/confirmation dependent on regulatory requirements and/or testing availability.

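### The 3-to-5-day liver retest in Protocol 9.4.7 is triggered by ALT, ALP or bilirubin but not by AST, so an isolated AST rise of >3 to 5 x ULN has no protocol-set repeat before the next scheduled chemistry

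*Protocol*

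**What the plan says.** Three parts of the protocol govern a raised aminotransferase.

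- **Holding drug (Section 8.1.1, Table JAIM.4).** Drug must be held when ALT or AST exceeds 5 x ULN. Among the conditions for resuming is "ALT and AST return to <2 x ULN and possible DILI has been ruled out". The section leaves the timing and frequency of retests to the investigator.
- **Considering a permanent stop (Section 8.1.2).** Seven liver criteria are listed, and stopping is to be "considered by the investigator when a patient meets one of the following conditions after consultation with the Lilly-designated medical monitor". Four of the seven concern aminotransferases, and each names ALT or AST. One of them is "ALT or AST >3 x ULN and either total bilirubin level (TBL) >2 x ULN or international normalized ratio >1.5". The other three concern ALP, for example "Alkaline phosphatase (ALP) >3 x ULN".
- **Early repeat (Section 9.4.7).** The trigger is "If a study patient experiences elevated ALT ≥ 3 x ULN, ALP ≥ 2 x ULN, or elevated TBL ≥ 2 x ULN". Liver tests should then be repeated within 3 to 5 days, "to confirm the abnormality and to determine if it is increasing or decreasing". The repeat panel includes AST and creatine kinase. The next step is conditional on what the repeat shows: "If the abnormality persists or worsens, clinical and laboratory monitoring should be initiated by the investigator and in consultation with the study medical monitor".

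Two appendices bear on discretion. Appendix 2 allows unscheduled chemistry if the investigator wishes. Appendix 4 lists further liver tests, PT/INR among them, under the wording "Selected tests may be obtained in the event of a treatment-emergent hepatic abnormality and may be required in follow-up with patients". The Schedule of Activities (Table JAIM.1) draws chemistry at every visit.

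**The concern.** Where the protocol decides whether to hold or stop drug, it gives AST the same standing as ALT. Where it decides whether to look again quickly, it drops AST and gives no reason. The purpose stated for the repeat, to see which way the value is moving, applies equally to AST. The step that brings in the medical monitor depends on the abnormality persisting or worsening, so for an isolated AST rise the rule never reaches it.

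At stake is the time before a site following the text learns whether such a value is climbing towards the hold threshold. Section 3.3 lists hepatotoxicity among the important potential risks and reports AST increases in the rheumatoid arthritis programme. The trial's primary objective is long-term safety.

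**Working it through.** **Step 1. Thresholds side by side.** Multiples of ULN, except INR.

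| Test | Lowest level used in 8.1.2 | Early-repeat trigger in 9.4.7 |
|---|---|---|
| ALT | >3, with a further feature | ≥3 |
| AST | >3, with a further feature | none |
| ALP | >2.5 with a further feature; >3 alone | ≥2 |
| Total bilirubin | >2, with a further feature | ≥2 |
| INR | >1.5, with ALT or AST >3 | none; not in the Appendix 2 panel |

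For ALT, ALP and bilirubin the repeat trigger sits at or below the lowest level at which 8.1.2 uses the test. AST appears in 4 of the 7 criteria in 8.1.2 and in 0 of the 3 triggers in 9.4.7.

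**Step 2. Which AST results are affected.**

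- AST >5 x ULN: the mandatory hold applies, and restart needs ALT and AST below 2 x ULN, so a repeat is implied. Two of the four AST criteria (>8 x; >5 x for more than 2 weeks after interruption) lie here.
- AST >3 x with bilirubin >2 x ULN: bilirubin triggers the 9.4.7 repeat by itself.
- AST >3 x with the listed symptoms or eosinophilia: already an 8.1.2 prompt, with medical monitor consultation.
- AST >3 to 5 x with ALT <3 x, ALP <2 x and bilirubin <2 x ULN, and no listed symptoms or eosinophilia: no interval is set. The remaining route into 8.1.2 is INR, which is measured only if someone chooses to order it.

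**Step 3. Time to the next scheduled chemistry.** Study days and windows are from Table JAIM.1. As a check, week = (study day − 1)/7 reproduces every visit week in the table, for example (421 − 1)/7 = 60 and (589 − 1)/7 = 84. Gap = difference in study days; range = gap ± the sum of the two visit windows.

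| Result drawn at | Next chemistry | Gap (days) | Range (days) |
|---|---|---|---|
| Week 4 (29 ± 4) | Week 12 (85 ± 7) | 85 − 29 = 56 | 56 ± 11 = 45 to 67 |
| Week 12 (85 ± 7) | Week 24 (169 ± 10) | 169 − 85 = 84 | 84 ± 17 = 67 to 101 |
| Weeks 24, 36, 48 (each ± 10) | 12 weeks later (± 10) | 84 | 84 ± 20 = 64 to 104 |
| Week 60 (421 ± 10) | Week 84 (589 ± 14) | 589 − 421 = 168 | 168 ± 24 = 144 to 192 |
| Weeks 84, 108, 132 (each ± 14) | 24 weeks later (± 14) | 168 | 168 ± 28 = 140 to 196 |

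Of the nine on-treatment chemistries from Week 4 to Week 132, one is followed by an 8-week gap, four by 12 weeks and four by 24 weeks. The longest range, 196 days, is 28 weeks. ALT at the same multiple is to be repeated in 3 to 5 days. After Week 156 the follow-up visit comes about 4 weeks after the last dose, and an early termination visit would shorten any of these gaps.

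**The case against.** A reader might infer that the protocol contradicts itself, or that a patient who should stop would be missed. The text supports neither. AST >3 to 5 x ULN alone is not a prompt in 8.1.2, and the 8.1.2 criteria call for a considered decision, not an automatic stop. The ALT repeat is itself worded as something that should be done, so the contrast is between a recommended interval and investigator judgement.

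Other safeguards are real. Investigators must document review of each laboratory report and must follow serious, medically important or drug-related events until they resolve or stabilise (Section 9.2). Hepatic events are of special interest (9.2.2). The sponsor reviews laboratory trends (9.4.8). Appendix 4 covers any treatment-emergent hepatic abnormality, whether or not 9.4.7 has been triggered. A careful site would probably repeat the test anyway.

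The omission may also be deliberate. The rule in 9.4.7 for collecting extra hepatic data likewise names ALT, bilirubin and ALP without AST. AST can rise from muscle, and creatine kinase is already in the scheduled panel. The 24-week gap is the worst case: by Week 60 former-placebo patients have had about 60 weeks of drug and former-active patients about 52 + 60 = 112. Section 3.3 says most liver test increases improved and no severe drug-induced liver injury was seen.

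All of this stands and limits the weight of the point. None of it supplies an interval: each safeguard permits a repeat without saying when. A single creatine kinase result helps to judge the source of an AST rise but does not show its direction.

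A reader might also want PT/INR made compulsory at every repeat, because the INR part of one criterion rests on an unscheduled test. That goes beyond the AST gap. Section 9.4.7 already points to Appendix 4, its list of repeat tests is not exhaustive, and the medical monitor is involved if the abnormality persists.

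**Conclusion.** The point holds in limited form. The protocol gives AST and ALT equal standing for holding or considering a stop, but only ALT starts the recommended 3-to-5-day repeat. For an isolated AST of >3 to 5 x ULN, no protocol-set repeat applies for 8, 12 or 24 weeks, depending on the visit.

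This assumes a site that does what the text sets and no more, visits on schedule within their windows, and no accompanying ALT, ALP or bilirubin trigger. The documents give no rate of isolated AST elevation, so the number of patients affected cannot be estimated. No missed automatic stop and no effect on any endpoint is claimed. It is a cheap improvement of low-to-moderate weight, worth making because it concerns a named potential risk in a long-term safety study.

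**What to change.** In Section 9.4.7, change the first trigger to ALT or AST ≥3 x ULN. Keep the ALP and bilirubin triggers, the 3-to-5-day interval and the repeat panel. Leave all thresholds in Sections 8.1.1 and 8.1.2 unchanged, and leave PT/INR available through Appendix 4 at the discretion of the investigator and medical monitor.

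The repeat for an isolated AST rise would then be due in 3 to 5 days, not at the next scheduled visit. The cost is amendment wording and an occasional extra blood draw. Some draws will be for AST of muscle origin, which the creatine kinase already in the panel helps to identify. No analysis changes.

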9.4.8. Safety Monitoring

Lilly will periodically review evolving aggregate safety data within the study by appropriate methods.

The Lilly-designated medical monitor will monitor safety data throughout the course of the study. Lilly will review SAEs within time frames mandated by company procedures. The Lilly-designated medical monitor will, as is appropriate, consult with the functionally independent Global Patient Safety (GPS) therapeutic area physician or clinical scientist and periodically review trends in safety data and laboratory analytes. Any concerning trends in frequency or severity noted by an investigator and/or Lilly or its designee may require further evaluation.

All deaths and SAE reports will be reviewed in a blinded manner by Lilly during the clinical trial. These reports will be reviewed to ensure completeness and accuracy, but will not be unblinded to Lilly during the clinical trial. If a death or clinical AE is deemed serious, unexpected, and possibly related to investigational product, only Lilly GPS will be unblinded for regulatory reporting and safety monitoring purposes. These measures will preserve the integrity of the data collected during this trial and minimize any potential for bias while providing for appropriate safety monitoring.

Investigators will monitor vital signs and carefully review findings that may be associated with cardiovascular events. Adverse event reports and vital signs will be collected at each study visit. The cardiovascular monitoring plan includes the following:

- Regular monitoring of lipid levels
- Potential MACE (cardiovascular death, myocardial infarction, stroke), other cardiovascular events (such as, hospitalization for unstable angina, hospitalization for heart failure, serious arrhythmia, resuscitated sudden death, cardiogenic shock, coronary interventions), venous thrombotic events and noncardiovascular deaths will be identified by the investigative site or through medical review and will be sent to a blinded Clinical Event Committee for adjudication at regular intervals.

9.4.9. Venous Thromboembolic Events

If a patient develops clinical features of a DVT or PE, appropriate local laboratory tests and imaging should be performed, as necessary, for the diagnosis of the event. For confirmed cases,

the patient will be discontinued from study treatment and additional laboratory testing is recommended as outlined in [Appendix 5](#). All suspected VTE events will be independently adjudicated by a blinded Clinical Event Committee.

9.5. Pharmacokinetics

Not Applicable.

9.6. Pharmacodynamics

Samples collected to measure PD markers, including, but not limited to, anti-dsDNA and complement will be identified by the patient number (coded) and retained at a facility selected by Lilly or its designee for a maximum of 1 year following last patient visit for the study.

9.7. Pharmacogenomics

9.7.1. *Whole Blood Samples for Pharmacogenetic Research*

Not applicable.

9.8. Biomarkers

Biomarker research is performed to address questions of relevance to drug disposition, target engagement, PD, mechanism of action, variability of patient response (including safety), and clinical outcome. Sample collection is incorporated into clinical studies to enable examination of these questions through measurement of biomolecules, including proteins, lipids, and other cellular elements.

Serum, plasma, and urine samples for biomarker research will be collected at the times specified in the Schedule of Activities (Section 2) where local regulations allow.

Samples will be used for research on the drug target, disease process, variable response to baricitinib, pathways associated with SLE, mechanism of action of baricitinib, and/or research method or in validating diagnostic tools or assay(s) related to SLE.

All samples will be coded with the patient number. These samples and any data generated can be linked back to the patient only by the investigator site personnel.

Samples will be retained at a facility selected by Lilly or its designee for a maximum of 15 years after the last patient visit for the study, or for a shorter period if local regulations and ERBs/IRBs impose shorter time limits. This retention period enables use of new technologies, response to regulatory questions, and investigation of variable response that may not be observed until later in the development of baricitinib or after baricitinib become(s) commercially available. Any samples remaining after 15 years will be destroyed.

9.9. Medical Resource Utilization and Health Economics

Health Economics and Medical Resource Utilization parameters will not be evaluated in this study.

10. Statistical Considerations

10.1. Sample Size Determination

It is expected that 80% of patients will complete Study JAHZ or JAIA and approximately 90% of patients who complete will enter Study JAIM; therefore, planned enrollment into JAIM from these originating studies will be approximately 1100 patients. Additional patients may enroll from addenda or other studies.

10.2. Populations for Analyses

For purposes of analysis of Study JAIM, the following populations are defined:

Population	Description
Modified intent to treat (mITT) Population	All patients who receive at least 1 dose of investigational product in Study JAIM will be included in the mITT population.
Safety Population	The safety population for JAIM is defined as all patients who receive at least 1 dose of investigational product in Study JAIM and who did not discontinue from the study for the reason 'Lost to Follow-up' at the first postbaseline visit.

10.3. Statistical Analyses

10.3.1. General Statistical Considerations

Statistical analysis of this study will be the responsibility of Lilly or its designee. A detailed SAP describing the statistical methodologies will be developed by Lilly or its designee.

Depending on the efficacy and health outcomes analysis, baseline may be defined as the last assessment prior to the first dose of active study drug in Study JAIM or as baseline from the originating study. Depending on the analysis, treatment groups can be based on assignment in JAIM, or could be further subdivided based on treatment group assignment in the originating studies.

Some of the efficacy and safety endpoints may be better assessed in the context of integrating data from the originating studies (and possibly other relevant studies). The SAP for this study and the SAPs which specify integrated analyses, will include details of which analyses will be performed on JAIM alone and which will be performed in an integrated fashion (including originating studies and possibly other studies). The exact definition of baseline, populations, and treatment groups will depend on the particular analysis (integrated vs. JAIM alone).

All tests of treatment effects will be conducted at a 2-sided alpha level of 0.05, unless otherwise stated. Adjustment for multiple comparisons will not be made.

Any change to the data analysis methods described in the protocol will require an amendment ONLY if it changes a principal feature of the protocol. Any other change to the data analysis methods described in the protocol, and the justification for making the change, will be described in the clinical study report. Additional exploratory analyses of the data will be conducted as deemed appropriate.

